7.5 STUDY REPORT

The primary analysis will be performed after all patients reach the 6 months follow up time point. Data will be analysed using the methods described in Section 7.4.

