2.3 PRIMARY AND SECONDARY ENDPOINTS

Primary Endpoint

The maintenance rate of immediate post-operative reduction position versus 3 week post-operative Re-displacement (Lateral reduction classification⁶):

- SubtypeP: Femoral head fragment fall down into diaphysis medullary space.
- SubtypeN: Even a little contact between femoral head fragment and anterior cortical bone.
- SubtypeA: Femoral head fragment located outside of medullary space..

[figure not shown]

Fig.3 Lateral reduction classification

Secondary Endpoint

- Surgery time
- Post-operative reduction position (AP3xML3)
- Pre-operative fracture classification and with or without open reduction
- CT assessment
- Safety evaluation

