2.4 ASSESSMENT PROCEDURE

The study assessment period will be 22 months, 18 months recruitment and 16 months follow-up. The follow-up for all patients will be at the following time points: baseline (preoperative), surgery, 3 weeks (+/- 3days) and 16 weeks (+/- 4 weeks)*.

*16 weeks assessment is optional item

A. Preoperative:

- a. Informed Consent
- b. Randomization
- c. Historical Record
- d. Fracture Classification (CT/X-ray)

B. Operative:

- a. Operative Form
 - i. Reduction (Open/ Closed)
 - ii. Surgery Time (reduction, from skin incision to closure)
 - iii. Implant Component Information (include diameter of sizer reamer)

C. Immediate postoperative and 3 week:

- a. CT Assessment
- b. Fracture Classification (If patient have not taken preoperative CT assessment)

D. 16 week (optional):

- a. CT Assessment
- b. Walking Ability

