2.6 ASSESSMENT TIMELINE/ SCHEDULE

Each follow-up visit time point will be determined based on the date of surgery. Each follow-up visit has a specific allowed time window:

- Preoperative
- Immediate Postoperative (after surgery within 3days)
- 3weeks (+/-3days)
- 16weeks* (-4weeks) *optional assessment

In the table below the retrieved information is per follow-up visit is found.

Assessment	Preop	Operative	3days	3weeks +/-3days	16weeks (- 4weeks)
Informed Consent	X				
Randomization	X				
Historical Record	X				

Operative Record		X			
Fracture type [CT/X-ray]	X		(X) ^{*1}		
CT assessment	(X)		X	X	(X)
Walking ability	(X) ^{*2}				(X)
Complications		As needed			

- () is optional assessment item.
- ^{*1} In the case of classified in X-ray in preoperative, reclassify the fracture type in postoperative CT.
- ^{*2} In the case of asking questionnaire impossibility, ask their preinjury walking ability in postoperative.

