5. ADVERSE EVENT MANAGEMENT AND REPORTING

Any adverse event should be documented on the Adverse Event case report form. A record of all adverse events, including details of the nature, onset, duration, severity, relationship to the device, relationship to the operative procedure and outcome, will be made on the relevant section(s) of the subject's CRF. The subject will be questioned about any adverse event(s) at each subsequent follow-up assessment visit.

Any serious adverse events (SAE/SADE/USADE) must be reported to head of institution and must be notified to other institutions participating in this study in accordance with Ethical Committee and Ethical Guidance for clinical study including human subject.

Adverse Event (AE):

An adverse event is any untoward medical occurrence in a patient receiving an investigational medical device that does not necessarily have to have a causal relationship with the device under investigation. An AE can therefore be any unfavorable and unintended sign (including abnormal laboratory finding), symptom, or condition temporally associated with the use of a medical device whether or not considered related to the medical device.

Serious Adverse Event (SAE):

A serious adverse event is an adverse event that

- a) led to death
 - b) led to a serious deterioration in the health of the patient that
 - c) led to fetal distress, fetal death or a congenital abnormality or birth defect
- 1) resulted in a life-threatening illness or injury

- 2) resulted in a permanent impairment of a body structure or a body function
- 3) resulted in medical or surgical intervention to prevent permanent impairment to body structure or body function
- 4) required in-patient hospitalization or prolongation of existing hospitalization

A planned hospitalization for a pre-existing condition, or a procedure required by this protocol, without serious deterioration in health, is not considered a serious adverse event.

Adverse Device Effect (ADE):

An ADE is any untoward and unintended response to an investigational medical device.

Serious Adverse Device Effect (SADE):

A SADE is any untoward and unintended response investigational medical device that has resulted in any of the consequences characteristic of a serious adverse event or that might have led to any of these consequences if suitable action had not been taken or intervention had not been made or if circumstances had been less opportune.

Unanticipated serious adverse device effect (USADE)

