7.4 DATA ANALYSES

Data will be analysed using SAS 9.0 or higher. The Type I error rate for the primary study analysis will be 0.05. Comparisons for secondary, exploratory, and safety analyses will be two-sided comparisons using $\alpha = 0.05$, with no adjustment for multiple comparisons.

Primary Analysis: The primary analysis will be performed on the set of patients with non-missing CT data at 3 weeks (Full Analysis Set (FAS)). Sensitivity analyses will be presented for the intention-to-treat (ITT) patient group. A two-tailed Pearson’s Chi-Square test at $\alpha = 0.05$ will be used to assess the study hypotheses and determine whether there is a statistically significant difference between investigational and control groups with regard to the maintenance rate of immediate post-operative reduction position.

Secondary Analysis: Analyses for secondary endpoints will be on the FAS, and will only use those cases with complete data for the endpoint being analysed.

Continuous data (e.g. age, BMI) will be reported using mean, standard deviation, median, and range. Comparisons between Investigational vs Control groups with regard to continuous baseline and secondary outcomes will be performed using standard statistical tests and will be chosen as appropriate for the scale and distribution of the measures being analyzed. For example, a t-test, Wilcoxon test, or one-way ANOVA (as appropriate) may be performed to assess differences in means/medians.

Categorical data (e.g. gender, classification of fracture) will be reported using frequency and percentage. Comparisons of Investigational vs Control with regard to categorical baseline, secondary and safety outcomes will be performed using standard statistical tests and will be chosen as appropriate for the scale and distribution of the measures being analyzed. For example, categorical outcomes may be compared for investigational and control groups using the Pearson’s chi-square test.

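### The 6-month time point in 7.5 is in no schedule and overruns the 22-month study, and the between-arm safety comparison rests on unequal follow-up and excludes patients without a 3-week CT

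*Combined protocol and SAP*

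**What the plan says.** **Timing of the analysis.** Section 7.5: "The primary analysis will be performed after all patients reach the 6 months follow up time point". The analysis then uses all the methods of 7.4.

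**Schedule.** The summary, 2.4 and 2.6 list preoperative, operative, immediate postoperative, 3-week and 16-week time points. Section 2.4 notes that "16 weeks assessment is optional item" and gives a window of 4 weeks either side. Section 2.6 has "16weeks* (-4weeks) *optional assessment", an earlier-only window. On duration, 2.4 says: "The study assessment period will be 22 months, 18 months recruitment and 16 months follow-up". The summary also gives 22 months in total.

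**Safety.** Section 2.3 lists "Safety evaluation" as a secondary endpoint, without naming events or a period. Section 5 says: "The subject will be questioned about any adverse event(s) at each subsequent follow-up assessment visit". It gives no end of reporting. The 2.6 table collects complications as needed, and section 9 reports them over the whole of data collection.

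**Safety analysis.** Section 7.4: "Comparisons of Investigational vs Control with regard to categorical baseline, secondary and safety outcomes will be performed using standard statistical tests", two-sided at 0.05. It places secondary endpoints on the FAS (patients with a non-missing 3-week CT) and says that these analyses "will only use those cases with complete data for the endpoint being analysed".

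**The concern.** The plan gives three lengths of follow-up (16 weeks, 6 months, 16 months), and only the first is in a schedule. Someone executing 7.5 as written would wait for a visit that nobody is asked to attend and that falls after the study's stated end.

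Safety is where this matters. Questioning about adverse events is tied to visits. After 3 weeks the only contact is optional, and no blinding of site staff is described, so attendance and questioning could differ by arm. Under 3.3, patients who miss follow-up are not counted as protocol deviations or as lost to follow-up, so a difference might go unnoticed. Comparing raw percentages would then mix event rates with attendance.

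The FAS rule raises a separate problem. Section 3.3 treats death and implant removal as withdrawal. A patient with either before the 3-week CT would have no such CT and would leave the safety comparison, although these are the outcomes that a safety table exists to count.

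**Working it through.** **1. Calendar check.** Inputs: 18 months of enrolment and 22 months in total (summary, 2.4); windows from 2.4 and 2.6. One month is 30.44 days, and surgery is taken as the date of enrolment.

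| Last patient reaches | Calculation | Study month |
|---|---|---|
| Close of 3-week window (21 + 3 = day 24) | 18 + 24/30.44 | 18.8 |
| 16 weeks (latest under 2.6) | 18 + 112/30.44 | 21.7 |
| 16 weeks + 4 (latest under 2.4) | 18 + 140/30.44 | 22.6 |
| 6 months (7.5) | 18 + 6 | 24 |
| 16 months (2.4) | 18 + 16 | 34 |

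The stated 22 months is reproduced by 16 weeks under the 2.6 window. The 2.4 window overruns it by 0.6 months, 7.5 by 2 months, and 16 months of follow-up by 12. Six months is 6 × 30.44/7 = 26.1 weeks: about 23 weeks after the last required visit and 10 after the optional one.

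**2. Primary analysis.** The endpoint is fixed at 3 weeks, so none of this enters it. With 87.5% v 72.7%, two-sided 5% and 80% power, the pooled-variance formula gives 114 per group against the plan's 113, and power at 113 is 79.98%. The sample size is not in dispute.

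**3. Events by length of observation.** The documents give no event rate. Assume 10% of patients have an event by 6 months (range 5 to 20%), with F(t) = 1 − exp(−H(t/26.1)^k), H = −ln(0.90), and k = 1 (constant hazard) or, in brackets, k = 0.5 (front-loaded).

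- F(3 weeks) = 1.20% [3.51%]; F(16 weeks) = 6.26% [7.92%]; F(6 months) = 10%.
- Expected patients with an event per 120: 1.4 [4.2], 7.5 [9.5], 12.
- Ratio of 16 weeks to 3 weeks: 6.26/1.20 = 5.2 [7.92/3.51 = 2.3]. Ratio of 6 months to 16 weeks: 10/6.26 = 1.6 [10/7.92 = 1.3].

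**4. Unequal attendance with equal hazards.** Suppose non-attenders' events are known only to 3 weeks. The observed risk in an arm with attendance a is a·F(16) + (1 − a)·F(3).

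- 90% attendance: 0.9 × 6.26 + 0.1 × 1.20 = 5.75% [7.48%].
- 80% attendance: 0.8 × 6.26 + 0.2 × 1.20 = 5.25% [7.04%]; ratio to the 90% arm 1.10 [1.06].
- 60% attendance: 0.6 × 6.26 + 0.4 × 1.20 = 4.24% [6.16%]; ratio 1.36 [1.21].

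Summing the exact binomial probabilities of all tables in which the Pearson chi-square is significant and favours the less-attended arm, with 113 per arm, gives the chance of a false excess:

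- 90% v 80%: 3.5% [3.5%].
- 90% v 60%: 6.9% [6.0%]. Across event rates of 5 to 20%: 4.8 to 12.0% [3.9 to 8.5%].

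The nominal figure is 2.5%.

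**5. FAS exclusion.** The plan allows for 5% attrition: 0.05 × 120 = 6 patients per arm. Under the assumptions in step 3, 1.4 [4.2] patients per arm have an event by 3 weeks. If even a few of those excluded are early deaths or implant removals, their loss is large against the number of events counted.

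**The case against.** - **Section 7.5 times the primary analysis. It does not say which adverse events count.** This stands. A reader might infer that 7.5 sets a 6-month safety period, or that the primary result depends on it; the text supports neither. The safety problem would remain if 7.5 were deleted.
- **The schedule points to 16 weeks as the intended end.** This also stands. It is the last listed visit and reproduces 22 months. The complications entry in the 2.6 table may be a merged cell running to the 16-week column that was lost in PDF reading. One might infer that events are counted with no end, over 6 to 24 months per patient. That is a strained reading in a study declared to last 22 months. But an intended end at 16 weeks does not give equal observation while that visit is optional.
- **The safety denominator is not undefined.** Correct: 2.3 makes safety a secondary endpoint, and 7.4 puts secondary endpoints on the FAS. The difficulty is what that population leaves out.
- **Chi-square is only an example in 7.4, and events can be recorded outside visits under section 5.** Both are true. The plan allows a better method but does not require one, and recording outside visits could shrink the gap modelled above without guaranteeing equal ascertainment.
- **Nothing suggests that attendance will differ by arm, and 90% v 60% is extreme.** Fair. At 90% v 80% the inflation is small. It is also tempting to say that event counts differ severalfold between any two windows; between 16 weeks and 6 months the ratio is only 1.6 [1.3].

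**Conclusion.** The concern holds as an inconsistency in the stated follow-up that needs correcting, together with a weakness in the safety comparison. The 6-month time point is in no schedule and ends 2 months after the stated study length, 16 months of follow-up cannot fit, and the two 16-week windows differ. As written, the safety comparison uses unequal observation times and removes patients without a 3-week CT.

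The primary estimate, type I error, sample size and power are untouched. The size of any safety bias cannot be read from the documents, because it rests on assumed event rates, hazard shape and attendance. Under those assumptions it runs from slight (3.5% against 2.5%) to moderate (6 to 7%, or up to 12% with a 20% event rate and 90% v 60% attendance). This should be corrected before the data are analysed, but it does not threaten the main conclusion.

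**What to change.** 1. In 7.5, replace 6 months with the scheduled time point that is meant; in 2.4, correct the 16 months. Adopt one 16-week window in 2.4 and 2.6, and check it against 22 months (21.7 under the 2.6 window, 22.6 under the 2.4 window). If 6-month follow-up really is intended, add it to both schedules and extend the stated duration.
2. In sections 5 and 7.4, define one safety period per patient, the same in both arms, that every patient is required to complete. With the current schedule this runs through the close of the 3-week window (day 24).
3. Make that comparison in all randomised patients who had surgery, not in the FAS.
4. Report later events by arm with follow-up time and the number contacted, as person-time rates or Kaplan-Meier estimates censored at last contact, without a test of raw percentages.

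**Cost.** This is a wording amendment, to be processed at up to 15 sites, with no change to the CT schedule, sample size or primary analysis. The drawback is that late harms listed in section 10, such as non-union and fatigue failure, are described but not formally tested. If the sponsor wants them tested, the alternative is a required adverse-event contact at 16 weeks, without CT: at most 240 contacts, fewer because some patients will attend anyway.

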8. DATA COLLECTION, HANDLING AND RETENTION

8.1 SOURCE DOCUMENTATION REQUIREMENTS

No source data will be available to the Sponsor of the study according to local law.

8.2 CASE REPORT FORMS (CRF)

Data for this clinical trial will be collected and documented on the subject Case Report Forms (CRFs) provided in an electronic form. Authorized study site personnel will complete the digital CRFs only. CRFs must be reviewed by the investigator or his/her designees.

8.3 STUDY DOCUMENT RETENTION

Study documents should be retained for 5 years after the study is complete.

9. DATA REPORTING

Within 6 months of the study close the sponsor will present a final study report to summarize all data collected throughout the study duration, complications throughout the course of the data collection, and general findings.

The report will contain the results of all primary and secondary endpoints. Also, patient follow-up will be analyzed throughout the data collection according to the following definition and equations:

- Lost To Follow-Up:
1. Death
 2. Implant Removal: Date of revision, all component part numbers removed, reason for revision, and any relation to study device.
 3. Revision of Components: date of revision, all component part numbers removed, and reason for revision Consent Rescinded

**Bearing revisions in which only the polyethylene is replaced will not be withdrawn from the study.*

Percentage Follow-up = # Patients with Follow-Up x 100
(Theoretically due – Lost To Follow-Up)

Percentage Accounted for = (# with Follow-Up + Lost To Follow-Up) x 100
Theoretically due

Both the sponsor and investigators will make reasonable efforts to publish the results of this trial.

10. RISK ANALYSIS

The following adverse event may occur.

- Wound infection
- Pain
- Nerve damage
- Damage of surrounding tissues
- Bone fractures
- Osteonecrosis
- Cardiovascular events(including thromboembolic events)
- Loss of reduction and/or fixation, implant migration
- Fatigue failure of implant
- Pseudoarthrosis, non-union, malunion, delayed or incomplete union
- Post-traumatic arthritis
- Inflammatory reaction
- Metal sensitivity
- Wear and/or corrosion of metal components

11. MONITORING PLAN

Zimmer Biomet, as the sponsor of this study, will monitor the data collection to ensure that the investigation is being conducted consistent with the protocol. The following describes the monitoring activities, which may take place during the course of the study.

11.1 FREQUENCY

Pre-Investigational Visit/Conference:

Prior to initiation of the study, the study manager will provide the investigator with all the necessary information to enable him to carry out his responsibilities. This prepares the site with an in-depth training on the protocol, case report forms, and data collection process for the length of the study. The study manager will also train the site on using the Zimmer Biomet Joint Assist database.

Monitoring of the Data

Monitoring of the data will occur at least annually, and as often as monthly.

11.2 SAMPLING PLAN

All data will be monitored for completeness and accuracy on at least an annual basis.

11.3 MONITORING TASKS

Zimmer Biomet will continually monitor the progress of the clinical trial. These activities include:

- Tracking of patient enrollment
- Review of all electronic patient data forms received by Zimmer Biomet for completeness
- Tracking of patients to ensure follow-ups are being completed at appropriate intervals
- Review of all adverse events
- Maintaining open communication with all investigational sites in order to ensure the quality of the clinical trial.
- In-house audits as needed

Upon completion of any type of monitoring, the site is responsible for resolving all discrepancies found in a timely manner. These will be sent to the site with an audit report by the study manager. All discrepancies found within the Joint Assist database will be queried and sent directly to the site. Delays in resolving queries are to be avoided at all costs; this provides the study with the most accurate data, prevents delay in reporting procedures & publication.

11.4 STUDY CLOSE-OUT

When a site has completed their data collection, a visit may be necessary by a Zimmer Biomet monitor to ensure all data has been obtained. Data will be reviewed for completeness, and monitored to ensure that all discrepancies have been resolved.

12. LABELING

The devices and products will be used in accordance with their instructions for use and/or approved labeling. The package insert for the device(s) in this study is included in the Investigator Binder.

13.ETHICAL AND REGULATORY REQUIREMENTS

13.1 CODE OF CONDUCT

The investigator will ensure that the clinical study is conducted in accordance with

1. Protocol
2. Ethical Guidance for clinical study including human subject (MHLW, Dec. 22, 2014)

13.2 INSTITUTIONAL REVIEW BOARDS/ETHICS COMMITTEE

The investigator must obtain appropriate Ethics Committee approval before the study can be initiated.

13.3 INFORMED CONSENT

Subjects (or the subject's legally authorized representative) will be provided with an informed consent and patient information sheet in order to give ample opportunity to review the consent and ask questions. The signed informed consent will be obtained before any study procedures begin. If the subject agrees to participate in the study, the subject/representative must sign the informed consent form. The witness and the investigator must also sign the informed consent form. A copy of the informed consent form should be given to the subject/representative. All subjects who meet all of the entry criteria will be considered for inclusion in this trial. Any subject meeting any of the exclusion criteria will be excluded from the trial.

The informed consent form must be approved by the institution's EC.

Subjects will be informed of new information learned during the study, which may affect the subject's decision to continue participation in the study.

An Informed Consent Log should be completed to document the existence of the signed informed consent form. The log will contain: Subject ID, date informed consent form signed, and the version signed.

13.4 SUBJECT CONFIDENTIALITY

The case report forms do not include any patient identifying information. Therefore, once the data is entered in the online database a patient can no longer be identified.

By assigning patients a unique ID number, their identity is protected in Joint Assist, the online database. The database is restricted, allowing a doctor to only view and enter data from his own patients. User

authentication is required to view research data. The data is transmitted to a centralized database through a secured (SSL) channel on the Internet. Data in transit is in 128-bit encryption. The access to the centralized database is limited to those who are responsible for maintaining the database.

14. PUBLICATION PLAN

Upon completion of all CT measurements and statistical analyses, representative investigator or the person who is designate by representative investigator, manuscript will be written in English or Japanese to meet peer-reviewed journal requirements.

